**Table 10 Treatment arms for imputation of tezepelumab participants under DRMI**

Reason for withdrawing from study	Reason for discontinuing IP	DRMI
Site terminated by sponsor		Tezepelumab
Study terminated by sponsor		Tezepelumab
Death		Placebo
Loss to follow-up	Subject lost to follow-up	Placebo by default (pending blinded review of any further information)
Withdrawal by subject	Subject decision	Placebo by default (pending blinded review of any further information)
Other	Severe non-compliance to protocol	Placebo
	Adverse event	Placebo
	Development of study-specific discontinuation criteria	Placebo
	Pregnancy	Placebo
	Other	Placebo by default (pending blinded review of any further information)

A blinded review of subjects who discontinued IP for reasons of “Subject lost to follow-up”, “Subject decision” or “Other” will be performed prior to unblinding at the primary database lock. A listing of these subjects and the assumptions made under DRMI will be documented. If any recorded comments (on either of the “Discontinuation of Investigational Product” or “Disposition” eCRF pages) indicate clearly that the reason for study withdrawal was not related to treatment, then the “Placebo” default for DRMI in the above table may be changed for that subject.

#### **4.2.6.4.3 Tipping point analysis**

If more than 5% of participants in either treatment group have missing data at Week 52, a tipping point analysis will also be performed. After Step 4 in Section [4.2.6.1](#), the following steps will be performed:

**Step 5.** The imputed values (for the missing values assuming MAR) in the tezepelumab group at Week 52 are added by a small positive amount  $\delta_t$  for each imputed dataset. The imputed values in the placebo group are subtracted by a small positive amount  $\delta_p$  for each imputed dataset.

**Step 6.** The change from baseline in the endpoint will be analysed using the same ANCOVA model used in the primary analysis. Then the SAS MIANALYZE procedure will be used to generate statistical inferences by combining results from the 100 analyses using Rubin’s formula.

Step 5 to Step 6 will be repeated iteratively until the p-value for treatment effect of tezepelumab compared to placebo estimated in Step 6 is  $>0.01$  and then  $>0.05$ . The LS mean difference between tezepelumab and placebo in change from baseline in co-primary endpoints at Week 52 and the corresponding p values will be provided for each combination of shift parameters. The value of  $\delta_t$  and  $\delta_p$  will be adjusted to avoid reaching the tipping point at the first iteration.

#### **4.2.6.5 Supportive analyses**

To facilitate the understanding of the co-primary endpoints, the empirical cumulative distribution function curves will be created for NPS and NCS at Week 52 by treatment group. The x-axis is the change from baseline and the y-axis is the percentage of participants. As described in Section [4.2.6.1](#), the post-surgery score is replaced by WPS and the post-SCS/biologic for NP score is replaced by WOCF. Participants who have missing change from baseline at WK52 without a preceeding surgery or SCS for NP will be excluded from this analysis.

#### **4.2.6.6 Subgroup Analyses**

To explore the treatment effect across categorical baseline or demographic variables as detailed in Section [3.1.6](#), a similar ANCOVA model, as described in Sections [4.2.6.1](#) and

[4.2.6.2](#), will be fitted, using imputed datasets, with additional factors for the relevant subgroup variable (based on eCRF, if data collected on an eCRF form) and its interaction with treatment. The estimate of the treatment effect and its 95% CI within each of the subgroup categories will be tabulated and also summarised graphically using a forest plot. A p-value for the treatment by subgroup interaction will not be presented for each of these models due to the exploratory nature of the analyses. If the subgroup variable is the same as a covariate, only the interaction term will be added. If the subgroup variable is a categorisation of the continuous baseline value (or re-classification of a categorical covariate), the categorical subgroup variable and interaction term will be added in the model, and the continuous baseline value (or categorical covariate) will be dropped from the model.

If any of the subgroups have fewer than 10 participants in one or both treatment groups, this subgroup level is not included in the model. If that leaves only one subgroup level, the model is not fitted for that categorical variable.

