9.4.2 Efficacy

9.4.2.1 Primary Endpoint(s)

For the primary estimand, data collected after surgery will be replaced with the worst possible score. Data collected after SCS will be replaced with the worst observation prior to the SCS (WOCF). Data collected after treatment discontinuation without surgery or SCS will be included in the analysis. For participants whose post-baseline data are all missing, the baseline value will be used in the analysis. For participants who discontinue the study without surgery or SCS, multiple imputation will be used to impute missing data assuming missing at random (MAR).

Each of the imputed datasets will be analysed using an analysis of covariance (ANCOVA) model with the baseline value as a covariate, and treatment group, baseline co-morbid asthma/AERD/NSAID-ERD status, prior surgery status, and regions as factors. Rubin's rule will be applied to combine analysis results (point estimates and standard errors) from the imputed datasets. Descriptive statistics including number of participants, mean, standard error, and least squares (LS) means will be provided for each time point. In addition, difference in LS means and the corresponding 95% confidence intervals (CIs) will be provided along with the p-values.

For the FDA and supplementary estimands, strategies for the ICEs are described in Sections [9.4.1.2](#) and [9.4.1.3](#) and will be applied accordingly. Additional sensitivity analyses will be performed to examine the MAR assumptions about missing data. Details of the supplementary and sensitivity analyses will be included in the SAP.

Subgroup analyses

For the purpose of exploring consistency of treatment effect across subgroups, a similar model will be fitted as for the primary analysis with additional factors for the relevant subgroup variable and its interaction with treatment. Key subgroups include:

- Age
- Gender
- Race
- Prior surgery status
- Allergic rhinitis
- Co-morbid asthma status
- AERD/NSAID-ERD
- Baseline eosinophil count
- Body mass index
- Region

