### 1.3 Number of Participants

Approximately 400 participants will be randomised to tezepelumab 210 mg Q4W or matching placebo in a 1:1 ratio.

The study is sized to provide compelling statistical evidence for the co-primary endpoints (NPS and NCS) and key secondary endpoints of change from baseline in loss of smell, LMK, and SNOT-22 (considering a significance level of 0.01 in the sample size calculations), as well as sufficient power to assess the composite endpoint of time to SCS and/or surgery (2-sided level of 1%). In addition, this sample size allows assessment of the effect of tezepelumab vs placebo on NPS and NCS in key subgroups and provides a reasonably-sized safety database (CSP Section 9.2).

Assuming a population standard deviation (SD) of 2.25 in total NPS change from baseline and 1.22 in NCS change from baseline, this sample size of 200 participants per arm will provide at least 95% total power to observe a statistically significant difference at a 2-sided 1% level on both co-primary endpoints if the true effect of tezepelumab is -1.8 in total NPS change from baseline and -0.87 in NCS change from baseline. The assumption of true effects is based on reported estimates in the dupilumab Phase III nasal polyp studies. It is expected that treatment with tezepelumab will demonstrate similar or better treatment effects over a 52-week period. The assumed SD was estimated based on the CIs of the corresponding endpoints in the dupilumab Phase III nasal polyp studies ([Bachert et al 2019](#)).

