#### **3.1.6 Subgroups**

The following subgroups are defined for the purposes of efficacy subgroup analysis.

- Age category at screening visit (<65,  $\geq$ 65 years)
- Gender at screening visit (male, female)
- Race at screening visit (white, non-white)
- Prior surgery for NP status (yes, no)
- Allergic rhinitis at screening visit (yes, no)
- Co-morbid asthma/AERD/NSAID-ERD status at screening visit (yes, no)
- AERD/NSAID-ERD at screening visit (yes, no)
- Baseline eosinophil count (<150,  $\geq$ 150 to <300,  $\geq$ 300 eosinophils/ $\mu$ L)
- Baseline BMI (< 30 kg/m^2,  $\geq$  30 kg/m^2)
- Region (China, Japan, ROW)
- Region (Asia Pacific including China and Japan, Europe, North America)
- Baseline NPS (<median,  $\geq$  median)
- Baseline NCS (< median,  $\geq$  median)
- Time since last NP surgery at screening visit (<3 years,  $\geq$ 3 years)
- Number of previous NP surgeries (0, 1, 2 or more)
- Prior SCS use for NP (yes, no)

- Baseline weight quartiles
- Baseline staphylococcus aureus colonization in nasal culture (yes, no, not applicable)
- Baseline eosinophil count quartiles
- Baseline total serum IgE quartiles
- Baseline perennial specific IgE status:
  - Any perennial FEIA positive: requires 1 or more specific IgE (FEIA) panels to be positive. Provided that at least one IgE panel is positive, no further requirement is made for data on all 7 panels for all countries, excluding China, and all 6 panels for China only to be available.
  - All perennial FEIA negative: requires all 7 specific IgE panels to be negative for all countries, excluding China, and all 6 specific IgE panels to be negative for China.
  - If there are fewer than 7 panels for all countries, excluding China and less than 6 panels for China with data available and none of these is positive, then IgE status is considered “Unknown perennial FEIA”.
  - Positive is defined as a value  $\geq 0.35$  kU/L.
  - The 7 panels for all countries, excluding China include: IgE American Cockroach, IgE Cat Dander, IgE D. farina, IgE D. pteronyssinus, IgE Dog Dander, IgE German Cockroach, and IgE Mould Mix 1..
  - The 6 panels for China only include: IgE Dog Dander, IgE Cat Dander, IgE D. farinae, D. pteronyssinus, IgE German Cockroach, and IgE Mould Mix 1.
- Baseline seasonal specific IgE status:

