**Step 4:** In the datasets from Step 3, replace post-surgery score with WPS, and replace post-SCS/biologic for NP score with WOCF. If a participant received both NP surgery and SCS for NP/biologic for NP, scores post-surgery will be set to WPS.

Each of the imputed datasets at Week 52 will be analysed using the analysis of covariance (ANCOVA) model with treatment group, baseline co-morbid asthma/AERD/NSAID-ERD status, prior surgery status, and region as factors (based on eCRF), and the baseline value as a covariate. Rubin’s rule will be applied to combine analysis results (point estimates and standard errors) from the imputed datasets using PROC MIANALYZE.

Descriptive statistics including number of participants, mean, standard error, and least squares (LS) means will be provided at Week 52. In addition, difference in LS means (using the observed marginal distribution of the sample covariates) and the corresponding 95% confidence intervals (CIs) will be provided along with the p-value. A single asterisk (\*) will be used to denote a result that is statistically significant at alpha = 0.05 and a double asterisk (\*\*) will be used to denote a result that is statistically significant at alpha = 0.01. Nominal p-values will be presented unless specified otherwise.

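### Two exploratory subgroup models replace the continuous baseline score with its own median split, which coarsens the adjustment and modestly widens the intervals for no gain

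*SAP*

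**What the plan says.** The primary ANCOVA (SAP 4.2.6.1) has treatment, co-morbid asthma/AERD/NSAID-ERD status, prior surgery and region as factors, "and the baseline value as a covariate". Protocol 9.4.2.1 describes the subgroup analysis as an extension of that model, with a treatment interaction included: "a similar model will be fitted as for the primary analysis with additional factors for the relevant subgroup".

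SAP 4.2.6.6 fits such models for both the primary and the US FDA estimand, with one exception. Where the subgroup is formed by cutting the baseline score into groups, "the categorical subgroup variable and interaction term will be added in the model". The same sentence then takes the underlying score out: "the continuous baseline value (or categorical covariate) will be dropped from the model". SAP 3.1.6 lists two subgroups of this kind, both split at the median: "Baseline NPS (<median" against at or above it, and "Baseline NCS (< median" against at or above it.

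The rule applies only where the subgroup categorises the baseline of the endpoint being modelled. It therefore reaches NPS by baseline NPS and NCS by baseline NCS. The crossed models (NPS by baseline NCS, NCS by baseline NPS) keep the continuous covariate.

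The results are within-category estimates with 95% intervals in a table and a forest plot. No interaction test is reported, and the SAP gives the reason: "A p-value for the treatment by subgroup interaction will not be presented for each of these models due to the exploratory nature".

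**The concern.** A two-level split treats everyone within a category as having the same baseline. If baseline predicts change, the unmodelled part goes into the residual variance and widens both within-category intervals. Chance imbalance between arms inside a category is also left unadjusted. These rows are the ones meant to show whether the effect varies with baseline severity, and they would rest on a coarser adjustment than neighbouring rows on the same plot.

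The plan's own scoring gives some reason to expect a link. Under the composite strategy, post-surgery NPS is set to 8 and NCS to 3. For those participants the change is exactly 8 or 3 minus baseline, a slope of -1.

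Estimation does not require the drop. The split and the continuous score are correlated, but that mainly affects the split's main effect. Treatment is randomised, so the within-category treatment contrasts remain estimable and valid with both terms in the model.

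**Working it through.** **Plan's own figures.** The SAP gives no figure for subgroup interval width. It does give the SDs used below: "Assuming a population standard deviation (SD) of 2.25 in total NPS change from baseline and 1.22 in NCS change from baseline" (SAP 1.3). They reproduce the power claim. With 200 per arm and 2-sided 1%:
- NPS: 1.8 / (2.25 × √(2/200)) = 8.00, and 8.00 − 2.576 = 5.42.
- NCS: 0.87 / (1.22 × √(2/200)) = 7.13, and 7.13 − 2.576 = 4.56.

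Power exceeds 0.9999 for each endpoint and jointly, so the stated 95% holds as a lower bound.

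**Other inputs.**
- Baseline NPS is 5 to 8: inclusion criterion 14 sets the floor and the scale sets the ceiling. The SAP derives NPS differently for eligibility and for efficacy, so a few analysed baselines could fall below 5.
- Baseline bi-weekly NCS is 2 to 3: inclusion criterion 15a and the scale.
- The slope b of change on baseline is in neither document. I assume an absolute size of 0.25 to 1.
- The baseline distribution is also not given. Several are assumed below.

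**Formula.** Let V be the baseline variance and B the part explained by the split. The interval width with the continuous score dropped, relative to keeping it beside the split, is

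√[(SD² − b²B) / (SD² − b²V)].

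**NPS, even over the integers 5 to 8.** The median is 6.5, so the split is {5,6} against {7,8}. V = 1.25 and B = 1.00, so the split keeps 80% of the baseline variance. SD² = 5.0625.
- b = 0.25: +0.2%.
- b = 0.5: √(4.8125 / 4.75) = 1.007, or +0.7%.
- b = 1: √(4.0625 / 3.8125) = 1.032, or +3.2%.

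With 100 per arm in a category and b = 1, the half-width is 1.96 × √(2/100) × residual SD: 0.541 with the continuous score kept, 0.559 with the split only, and 0.624 with no baseline term at all.

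**NPS, uneven split.** The rule is below the median against at or above it, so ties can make the categories unequal. If the median is 6, the split is {5} against {6,7,8}. Three assumed distributions over 5, 6, 7 and 8:

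| Probabilities | V | B | b = 0.5 | b = 1 |
|---|---|---|---|---|
| 0.40, 0.30, 0.20, 0.10 | 1.000 | 0.667 | +0.9% | √(4.396/4.063): +4.0% |
| 0.30, 0.30, 0.20, 0.20 | 1.210 | 0.724 | +1.3% | √(4.338/3.853): +6.1% |
| 0.15, 0.40, 0.25, 0.20 | 0.950 | 0.397 | +1.4% | √(4.665/4.113): +6.5% |

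**NCS, even over 2 to 3.** V = 1/12 = 0.0833 and B = 0.0625, so the split keeps 75%. SD² = 1.4884.
- b = 0.25: +0.04%.
- b = 0.5: +0.2%.
- b = 1: √(1.4259 / 1.4051) = 1.007, or +0.7%.

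**Simulation.** The interaction ANCOVA was simulated with 400 participants and 2,000 runs, on the even baselines, at slopes 0.25, 0.5 and 1. Widening was 0.0%, 0.6% and 3.1% for NPS, and −0.1%, 0.0% and 0.6% for NCS, in line with the formula.

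**Without the entry restriction.** For a normal baseline the split keeps 2/π = 64%, and the ratio is √[(1 − 0.637ρ²)/(1 − ρ²)]. Widening is +0.8% at a correlation of 0.2, +1.8% at 0.3, +5.9% at 0.5 and +16% at 0.7.

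**The case against.** The strongest reply is that this is a valid, pre-specified simplification on which no decision turns. The rule is explicit and leaves no analyst discretion. Randomisation protects the treatment contrasts under the simpler model. The analyses are exploratory, and baseline NPS and NCS are not among the key subgroups in protocol 9.4.2.1. All of that stands, and it limits the point to precision.

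A reader might also draw stronger conclusions, which the documents do not support:
- **That the main prognostic covariate is discarded.** Neither document ranks baseline as the main predictor, and the median split remains in the model. Under the even baselines above it keeps 75% to 80% of the baseline variance.
- **That the loss is large.** Widening of 16% needs an unrestricted normal baseline with a correlation of 0.7. Entry criteria narrow the range: with even baselines and a slope of 1, R² is 1.25/5.0625 = 0.25 for NPS and 0.0833/1.4884 = 0.06 for NCS. An extreme two-point skew at slope 1 gives 15% for NPS and 4.7% for NCS, but only if tied scores are shared between the two categories, which the SAP's rule for tied NPS values does not do.
- **That the SAP contradicts the protocol.** The protocol promises a similar model, not an identical one. Dropping a covariate sits less well with its wording about additional factors, but that is a looser fit, not a conflict.

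The reply does not identify any benefit from dropping the continuous score.

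**Conclusion.** The point holds as a minor matter of precision. In two exploratory models per estimand the continuous baseline is coarsened to a median split, although keeping both terms is estimable and uses data already collected. The cost is unadjusted chance imbalance within categories and slightly wider 95% intervals: about 0.2% to 3% for NPS with an even 5-to-8 baseline, up to about 4% to 7% if ties make the split uneven and the slope is 1, and under 1% for NCS in most cases.

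These sizes rest on assumed slopes and baseline distributions, because the documents give neither. The direction does not depend on them: if baseline predicts change within categories, the split-only model is less precise. If it does not, keeping the score costs one degree of freedom.

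Nobody should infer bias in the subgroup estimates or any effect on the primary analysis, type I error or power. None follows.

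**What to change.** Amend the last sentence of the first paragraph of SAP 4.2.6.6. When the subgroup categorises the continuous baseline value, keep that value in the model alongside the categorical subgroup and its interaction with treatment. Drop a covariate only when the subgroup re-classifies a categorical factor, as with number of previous surgeries or the alternative region grouping.

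The cost is one sentence and one extra term in two models per estimand, with no new data. It should be done before primary database lock, because SAP 2.1.4 says the SAP will not be updated after that. Later, the fuller model could only be reported as an additional analysis described in the CSR.

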## **4.2.7 Key Secondary Endpoints**

### **4.2.7.1 Primary Analysis**

For all the key secondary endpoints, a single asterisk (\*) will be used to denote a result that is statistically significant at alpha = 0.05 and a double asterisk (\*\*) will be used to denote a result that is statistically significant at alpha = 0.01. Nominal p-values will be presented unless specified otherwise. Analyses based on the primary estimand and US FDA primary estimand will be provided for key secondary endpoints when applicable, unless noted otherwise.

#### **4.2.7.1.1 Change from baseline in loss of smell at Week 52**

The change from baseline in loss of smell at Week 52 will be analysed using the methods as described in Sections [4.2.6.1](#) (primary estimand) and [4.2.6.2](#) (US FDA primary estimand).

#### **4.2.7.1.2 Change from baseline in SNOT-22 at Week 52**

The same methods as described in Sections [4.2.6.1](#) (primary estimand) and [4.2.6.2](#) (US FDA primary estimand) will be applied.

#### **4.2.7.1.3 Change from baseline in LMK at Week 52**

The same methods as described in Sections [4.2.6.1](#) (primary estimand) and [4.2.6.2](#) (US FDA primary estimand) will be applied.

#### **4.2.7.1.4 Time to first nasal polyp surgery decision and/or SCS for NP up to Week 52**

Time to first SCS for NP or decision to have surgery for NP during the 52-week treatment period will be analysed using a Cox proportional hazards model, adjusting for treatment, baseline co-morbid asthma/AERD/NSAID-ERD status, prior surgery status, and region (based on eCRF). The event of interest is the first SCS for NP or nasal polyp surgery decision, whichever is earlier if both occur. Hazard ratios, corresponding 95% CIs, and p-values will be

presented. The proportion of participants with the decision of NP surgery or who took SCS for NP up to week 52 will be estimated using the Kaplan-Meier method. The point estimate and 95% CI will be presented. Kaplan-Meier curves will be generated.

#### **4.2.7.1.5 Time to first surgery decision for NP up to Week 52**

The same method described in Section 4.2.7.1.4 will be used to analyse the time to first surgery decision for NP.

#### **4.2.7.1.6 Time to first SCS for NP up to Week 52**

The same method described in Section 4.2.7.1.4 will be used to analyse the time to first SCS for NP.

#### **4.2.7.1.7 Change from baseline in NPSD TSS at Week 52**

The same methods as described in Sections 4.2.6.1 (primary estimand) and 4.2.6.2 (US FDA primary estimand) will be applied.

#### **4.2.7.1.8 Change from baseline in pre-BD FEV1 at Week 52 (comorbid asthma/AERD/NSAID-ERD subset)**

Observed pre-BD FEV1 data will be used in the analysis regardless of NP surgery and SCS/biologic for NP. Missing data up to Week 52 will be imputed assuming MAR. The intermittent missing data will be imputed using the MCMC method in SAS PROC MI with an IMPUTE=MONOTONE statement for each treatment group separately. The imputation model will include prior NP surgery status, region, baseline pre-BD FEV1 value, and data at each timepoint (both prior NP surgery status and region will be based on eCRF). 100 imputed datasets will be generated. The remaining monotone missing data will be imputed using the MI procedure with the 'MONOTONE REG' option for each treatment group separately. The imputation model will include baseline value, prior surgery status, region, and data at each timepoint. A random seed of 539612 will be used for both monotone and non-monotone imputations.

The same ANCOVA model described in Section 4.2.6.1 will be used at Week 52. Descriptive statistics including number of participants, mean, standard error, and LS means will be provided. In addition, the difference in LS means and the corresponding 95% CI will be provided along with the p-value.

